5.1.5 Study Diagram

Abbreviations: n=number of participants; RP2D = recommended Phase 2 dose.

Figure 6 Study Diagram

5.2 Number of Participants

A maximum of approximately 220 participants will be enrolled (Parts 1 and 2). A target sample size of 159 participants will be used for trial planning purposes.

5.3 Beginning and End of Study Definition

The overall trial begins when the first participant signs the informed consent form (ICF). The overall trial ends when the last participant completes the last study-related phone-call or visit, withdraws from the trial or is lost to follow-up (i.e. the participant is unable to be contacted by the investigator).

Once the participant has achieved the study objective or study has ended, the participant is discontinued from this study and may be enrolled in an extension study to continue protocol-defined assessments and treatment.

5.3.1 Clinical Criteria for Early Trial Termination

Early trial termination will be the result of the criteria specified below:

1. Quality or quantity of data recording is inaccurate or incomplete
2. Poor adherence to protocol and regulatory requirements

3. Incidence or severity of adverse drug reaction in this or other studies indicates a potential health hazard to participants
4. Plans to modify or discontinue the development of the study drug

In the event of Sponsor decision to no longer supply study drug, ample notification will be provided so that appropriate adjustments to participant treatment can be made.

A primary objective of this early Phase I trial is to identify the maximum safe and well-tolerated dose and/or dosing regimen that achieve pharmacokinetic, pharmacodynamic and/or biologic targets in humans based on preclinical or early clinical data. Therefore, it is possible that trial participants may not receive all doses specified in the protocol if this objective is achieved at lesser dose levels in this trial. This would not be defined as early termination of the trial, but rather an earlier than anticipated achievement of the trial objective(s). If a finding (eg, pharmacokinetic, pharmacodynamic, efficacy, biologic targets, etc.) from another preclinical or clinical trial using the study treatment(s), comparator(s), drug(s) of the same class, or methodology(ies) used in this trial, results in the trial(s) or program being stopped for non-safety reasons, this also does not meet the definition of early trial termination.

Early trial termination is defined as a permanent discontinuation of the trial due to unanticipated concerns of safety to the trial participants arising from clinical or preclinical trials with the study treatment(s), comparator(s), drug(s) of the same class or methodology(ies) used in this trial.

5.4 Scientific Rationale for Study Design

5.4.1 Rationale for Endpoints

5.4.1.1 Efficacy Endpoints

This trial will use ORR based on RECIST 1.1 as assessed by investigator as the secondary endpoint. RECIST 1.1 is a validated tool in assessing anti-cancer activity of an investigational agent.

Exploratory endpoints include DCR, DOR, and PFS as assessed by the investigator based on RECIST 1.1, ORR, DOR, DCR, and PFS as assessed by the investigator based on iRECIST as well as OS for each cohort.

A central imaging vendor will be used to collect, clean, and hold tumor imaging. Images will be collected for possible analysis by blinded, independent central review.

5.4.1.2 Safety Endpoints

The primary safety endpoint is the incidence of DLTs. Safety and tolerability will be assessed by clinical review throughout the trial. The toxicities and grades experienced by participants who have received study treatment, including AEs, SAEs and ECIs will be summarized. Other safety measures evaluated in study include laboratory tests, ECGs, ECHO/MUGA, vital signs, ECG measurements, physical examinations, and eye examination.

5.4.1.3 Pharmacokinetic Endpoints

Binimetinib was found to be a weak inhibitor of human liver microsomal UGT1A-mediated SN-38 conjugation, with an IC_{50} value greater than 25 μ M. Irinotecan (pro-drug) is a substrate of extensive metabolic conversion by various enzyme systems, including carboxylesterases to form the active metabolite SN-38, and UGT1A1 mediating glucuronidation of SN-38 to form the inactive glucuronide metabolite SN-38G. The effects of binimetinib on the PK of irinotecan and SN-38, conversely, to estimate the effects of irinotecan and SN-38 on the PK of binimetinib will be explored. Blood samples of binimetinib, irinotecan and SN-38 will be obtained to measure PK of binimetinib, irinotecan, and SN-38.

5.4.1.4 Pharmacodynamic Endpoints

Not applicable.

5.4.1.5 Planned Exploratory Biomarker Research

[figure not shown]
Cancer immunotherapies represent an important and novel class of antitumor agents. However, the mechanism of action of these exciting new therapies is not completely understood and much remains to be learned regarding how best to leverage these new drugs in treating participants. Thus, to aid future participants, it is important to investigate the determinants of response or resistance to cancer immunotherapy, as well as determinants of AEs in the course of our clinical trials. These efforts will identify novel predictive/PD biomarkers and generate information that will better guide single-agent and combination therapy with immuno-oncology drugs. To identify novel biomarkers, biospecimens (ie, blood components, tumor material) will be collected to support analyses of cellular components (eg, protein, DNA, RNA, metabolites) and other circulating molecules.

Investigations may include but are not limited to:

- Germline (blood) genetic analyses (eg, SNP analyses, whole exome sequencing, whole genome sequencing): This research will evaluate whether genetic variation within a clinical trial population correlates with response to the treatment(s) under evaluation. CCI
CCI
[REDACTED]
- Genetic (DNA) analyses from tumor: The application of new technologies, such as next generation sequencing, has provided scientists the opportunity to identify tumor-specific DNA changes (eg, mutations, methylation status, MSI). Key molecular changes of interest to immune-oncology drug development include (for example) the mutational burden of tumors and the clonality of T-cells in the tumor microenvironment. Increased mutational burden (sometimes referred to as a “hyper-mutated” state) may generate neo-antigen presentation in the tumor microenvironment. To conduct this type of research, it is important to identify tumor-specific mutations that occur across all genes in the tumor genome. Thus, genome wide approaches may be used for this effort. Note that in order to understand tumor-specific mutations; it is necessary to compare the tumor genome with the germline genome.

[figure not shown]
- Pretreatment and posttreatment tumor (when obtained) and blood samples collected in this study may undergo proteomic, genomic and transcriptional analyses (both DNA and RNA analyses). Additional research may evaluate factors important for predicting responsiveness or resistance to binimetinib and pembrolizumab combination therapy and other immunologic targets. CCI

CCI

- Tumor and blood RNA analyses: Both genome-wide and targeted mRNA expression profiling and sequencing in tumor tissue and in blood may be performed to define gene signatures that correlate to clinical response to treatment with pembrolizumab or other immunotherapies. CCI

CCI

- Proteomics and IHC using blood or tumor: tumor and blood samples from this study may undergo proteomic analyses (eg, PD-L1 IHC). CCI

CCI

CCI Tumor tissue may, therefore, be subjected to proteomic analyses using a variety of platforms that could include but are not limited to immunoassays and liquid chromatography/mass spectrometry. This approach could identify novel protein biomarkers that could aid in participant selection for pembrolizumab therapy.

- Other blood derived biomarkers: In addition to expression on tumor tissue, PD-L1 and other tumor derived proteins can be shed from tumors and released into the blood. Assays such as enzyme-linked immunoassay measure such proteins in serum. Correlation of expression with response to pembrolizumab therapy may identify new approaches for predictive biomarkers in blood, representing a major advance from today's reliance on assessing tumor biomarkers. This research would serve to develop such assays for future clinical use.

5.4.1.5.1 Planned Genetic Analysis

Genetic variation may impact a participant's response to therapy, susceptibility to, and severity and progression of disease. Variable response to therapy may be due to genetic determinants that impact drug absorption, distribution, metabolism, and excretion; mechanism of action of the drug; disease etiology; and/or molecular subtype of the disease

being treated. Therefore, where local regulations and IRB/IEC allow, a sample will be collected for DNA analysis from consenting participants.

DNA samples will be used for research related to the study treatment(s), the disease under study and related diseases. They may also be used to develop tests/assays including diagnostic tests related to the disease under study, related diseases and study drug(s). Genetic research may consist of the analysis of 1 or more candidate genes or the analysis of genetic markers throughout the genome [or analysis of the entire genome] (as appropriate). DNA samples will be analyzed for variation across the entire genome. Analyses may be conducted if it is hypothesized that this may help further understand the clinical data. The samples may be analyzed as part of a multi-study assessment of genetic factors involved in the response to understand study disease or related conditions.

5.4.1.6 Microsatellite Instability Testing

Mismatch repair proteins, or MSI loci testing for CRC is already clinically indicated as per NCCN [National Comprehensive Cancer Network 2017], ESMO [Van Cutsem, E., et al 2016], and ASCO guidelines [Sepulveda, A. R., et al 2017]. MMR or MSI status will be performed locally. Archived tumor samples or newly obtained biopsies will be used for determining MSI/MMR status by the site's local laboratory.

MMR or MSI status is determined by examining either 1) protein expression by IHC of 4 MMR enzymes (MLH1/MSH2/MSH6/PMS2) or 2) 5 tumor microsatellite loci using PCR-based assay, respectively.

Tumors are classified as MSI-H when at least 2 allelic shifts among the 5 analyzed microsatellite markers are detected by PCR, or absence of at least 1 of 4 MMR proteins expression is detected by IHC (also called mismatch repair deficient, dMMR). Confirmation of non-MSI-H/pMMR status by one testing method (either PCR or IHC) is sufficient for eligibility. However, both methods should indicate pMMR and non-MSI-H status in participants who had both tests done. Sponsor consultation is required if further investigation led to confirmation of pMMR/non MSI-H status by the investigator.

5.4.1.7 Future Biomedical Research

The Sponsor will conduct Future Biomedical Research on specimens consented for future biomedical research during this clinical trial. This research may include genetic analyses (DNA), gene expression profiling (RNA), proteomics, metabolomics (serum, plasma) and/or the measurement of other analytes, depending on which specimens are consented for future biomedical research.

Such research is for biomarker testing to address emergent questions not described elsewhere in the protocol (as part of the main trial) and will only be conducted on specimens from appropriately consented participants. The objective of collecting/retaining specimens for Future Biomedical Research is to explore and identify biomarkers that inform the scientific understanding of diseases and/or their therapeutic treatments. The overarching goal is to use such information to develop safer, more effective drugs/vaccines, and/or to ensure that participants receive the correct dose of the correct drug/vaccine at the correct time. The details of Future Biomedical Research are presented in Appendix 7 – Collection and Management of Specimens for Future Biomedical Research.

5.4.2 Rationale for The Use of Comparator/Placebo

This study does not include comparators or placebo.

5.5 Justification for Dose

5.5.1 Starting Dose for This Trial

5.5.1.1 Justification for Treatment Regimen

5.5.1.1.1 Rationale for Fixed Dose Pembrolizumab

The planned dose of pembrolizumab for this study is 200 mg every 3 weeks (Q3W). Based on the totality of data generated in the Keytruda development program, 200 mg Q3W is the appropriate dose of pembrolizumab for adults across all indications and regardless of tumor type. As outlined below, this dose is justified by:

- Clinical data from 8 randomized studies demonstrating flat dose- and exposure-efficacy relationships from 2 mg/kg Q3W to 10 mg/kg every 2 weeks (Q2W),
- Clinical data showing meaningful improvement in benefit-risk including overall survival at 200 mg Q3W across multiple indications, and
- Pharmacology data showing full target saturation in both systemic circulation (inferred from pharmacokinetic [PK] data) and tumor (inferred from physiologically-based pharmacokinetic [PBPK] analysis) at 200 mg Q3W

Among the 8 randomized dose-comparison studies, a total of 2262 participants were enrolled with melanoma and NSCLC, covering different disease settings (treatment naïve, previously treated, PD-L1 enriched, and all-comers) and different treatment settings (monotherapy and in combination with chemotherapy). Five studies compared 2 mg/kg Q3W versus 10 mg/kg Q2W (KN001 Cohort B2, KN001 Cohort D, KN002, KN010, and KN021), and 3 studies compared 10 mg/kg Q3W versus 10 mg/kg Q2W (KN001 Cohort B3, KN001 Cohort F2 and KN006). All of these studies demonstrated flat dose- and exposure-response relationships across the doses studied representing an approximate 5- to 7.5-fold difference in exposure. The 2 mg/kg (or 200 mg fixed-dose) Q3W provided similar responses to the highest doses studied. Subsequently, flat dose-exposure-response relationships were also observed in other tumor types including head and neck cancer, bladder cancer, gastric cancer and classical Hodgkin Lymphoma, confirming 200 mg Q3W as the appropriate dose independent of the tumor type. These findings are consistent with the mechanism of action of pembrolizumab, which acts by interaction with immune cells, and not via direct binding to cancer cells.

Additionally, pharmacology data clearly show target saturation at 200 mg Q3W. First, PK data in KN001 evaluating target-mediated drug disposition (TMDD) conclusively demonstrated saturation of PD-1 in systemic circulation at doses much lower than 200 mg Q3W. Second, a PBPK analysis was conducted to predict tumor PD-1 saturation over a wide range of tumor penetration and PD-1 expression. This evaluation concluded that pembrolizumab at 200 mg Q3W achieves full PD-1 saturation in both blood and tumor.

Finally, population PK analysis of pembrolizumab, which characterized the influence of body weight and other participant covariates on exposure, has shown that the fixed-dosing

provides similar control of PK variability as weight based dosing, with considerable overlap in the distribution of exposures from the 200 mg Q3W fixed dose and 2 mg/kg Q3W dose. Supported by these PK characteristics, and given that fixed-dose has advantages of reduced dosing complexity and reduced potential of dosing errors, the 200 mg Q3W fixed-dose was selected for evaluation across all pembrolizumab protocols.

5.5.1.1.2 Binimetinib Starting Dose

The starting dose of binimetinib will be 30 mg oral BID and the dose will be escalated to 45 mg oral BID per the mTPI rule. Rationale for these doses is based on studies conducted in patients with solid tumors. ARRAY-162-111 was a Phase I, open-label, dose-escalation study of oral binimetinib in patients with advanced solid tumors followed by expansion cohorts in patients with advanced or metastatic biliary cancer or KRAS- or BRAF-mutant mCRC. A total of 93 participants received at least 1 dose of binimetinib. Nineteen patients with advanced solid tumors received binimetinib in the dose-escalation phase. Four dose levels were evaluated: 30 mg BID, 45 mg BID, 60 mg BID and 80 mg BID. Two of the 4 participants receiving 80 mg BID experienced DLTs (Grade 3 chorioretinopathy and Grade 3 dermatitis acneiform despite maximal treatment measures), thus the 80 mg BID dose was declared non-tolerable. Seven participants were enrolled at 60 mg BID and no DLTs were observed, therefore, 60 mg BID was declared the MTD. Following completion of the Dose-escalation Phase, a total of 74 participants were enrolled in the Expansion Phase, 28 participants in the biliary cancer cohort, 31 participants in KRAS-mutant CRC cohort and 15 participants in the BRAF-mutant CRC cohort. After initiation of the Expansion Phase, a higher-than-expected frequency of ocular AEs affected the ability to treat participants continuously at the MTD, thus a reduced dose of 45 mg BID was implemented for the remainder of newly enrolled participants in the expansion phase cohorts.

Study CMEK162X1101 was an open-label, dose escalation, Phase I study of binimetinib as a single agent in Japanese participants with advanced solid tumors with the expansion part in participants whose tumors harbored RAS or BRAF mutations. Twenty-one participants were enrolled and treated with at least 1 dose of binimetinib (6 participants with 30 mg BID and 15 participants with 45 mg BID). Dose-limiting toxicities were reported during the dose escalation part for determination of the MTD. A total of 2 participants in the 45 mg BID dose level cohort reported 2 DLTs, both of which were recurrent Grade 2 detachment of retinal pigment epithelium. These events were judged as DLTs due to recurrence of the toxicity at the same grade while the dose of study drug was reduced. Therefore, 45 mg BID was declared the MTD in Japanese participants. No DLT was reported in participants enrolled in the expansion part.

In addition, a Phase I study evaluated binimetinib 30 mg BID and 45 mg BID dose in combination with mFOLFOX7 in heavily treated metastatic CRC patients (Section 5.5.1.1.2), and these 2 doses of binimetinib were well tolerated. Taken together, 30 mg BID and 45 BID doses are appropriate doses to be explored in the current trial [Thet Cho, M., et al 2016].

5.5.1.1.3 mFOLFOX7 Starting Dose

The starting dose of mFOLFOX7 (oxaliplatin 85 mg/m² IV infusion, leucovorin 400 mg/m² IV infusion, 5-FU 2400 mg/m² IV infusion over 46 to 48-hour infusion) Q2W, which is

considered a globally accepted SOC [National Comprehensive Cancer Network 2017] [Hochster, H. S., et al 2014].

5.5.1.1.4 FOLFIRI Starting Dose

The starting dose of FOLFIRI (irinotecan 180 mg/m² IV over 30-90 minutes, leucovorin 400 mg/m² IV infusion, 5-FU 2400 mg/m² IV over 46 to 48-hour infusion) Q2W, which is considered globally accepted SOC [National Comprehensive Cancer Network 2017].

5.5.2 Maximum Dose/Exposure for This Trial

The dose of pembrolizumab will be 200 mg administered intravenously Q3W and will remain constant.

The dose of pembrolizumab is based on single agent doses tested as well as the highest doses tested in combination in Phase I to II trials (See Section 5.5.1.1 and package insert for KEYTRUDA™).

The maximum dose of binimetinib for this trial will be 45 mg administered orally BID (maximum 90 mg total per day). The maximum dose of binimetinib is based on the single agent doses tested in participants with advanced solid tumors followed by expansion cohorts in participants with advanced or metastatic biliary cancer of KRAS-or BRAF-mutant mCRC in Study ARRAY-162 [Thet Cho, M., et al 2016] (See Section 5.5.1.1.2).

The maximum dose of mFOLFOX7 and FOLFIRI is the starting dose as outlined in Sections 5.5.1.1.3 and 5.5.1.1.4, respectively.

6. Study Population

Male and female participants with non-MSI-H/pMMR mCRC will be enrolled in this trial.

Prospective approval of protocol deviations to recruitment and enrollment criteria, also known as protocol waivers or exemptions, is not permitted.

6.1 Inclusion Criteria

Participants are eligible to be included in the study only if all of the following criteria apply:

1. Male and female participants who are at least 18 years of age on the day of signing consent will be eligible for enrollment in the study.
2. Have a histologically-confirmed, unresectable or metastatic (Stage IV American Joint Committee on Cancer seventh edition) CRC.
3. Have a locally determined non-MSI-H/pMMR tumor status (Section 5.4.1.6).
4. Have at least 1 radiologically measurable lesion as defined by RECIST 1.1.
5. Have an ECOG performance status of 0 or 1 prior to treatment initiation.
6. Have a life expectancy of at least 3 months.

7. Participants must have the ability to swallow and retain oral medication and not have any clinically significant gastrointestinal abnormalities that might alter absorption.
8. Have adequate organ function as defined in **Table 4**. All screening labs should be performed within 10 days prior to the first dose of trial treatment.

Table 4 Inclusion Criteria Laboratory Parameters

Hematological	
Absolute neutrophil count (ANC)	$\geq 1,500/\text{mcL}$
Platelets	$\geq 100,000/\text{mcL}$
Hemoglobin	$\geq 9.0 \text{ g/dL}$ or $\geq 5.6 \text{ mmol/L}$
Renal	
Serum creatinine OR Calculated* serum creatinine clearance (GFR can be used in place of creatinine or creatinine clearance)	$\leq 1.5 \times$ upper limit of normal (ULN) OR $\geq 60 \text{ mL/min}$ for participants with creatinine levels $>1.5 \times$ institutional ULN
Hepatic	
Serum total bilirubin	$\leq 1.5 \times$ ULN or direct bilirubin \leq ULN for participants with total bilirubin >1.5 ULN
AST (SGOT) and ALT (SGPT)	$\leq 2.5 \times$ ULN OR $\leq 5.0 \times$ ULN for participants with liver metastases
Albumin	$\geq 3.0 \text{ g/L}$
Coagulation	
International Normalized Ratio (INR) or prothrombin time (PT) or activated partial thromboplastin time (aPTT)	$\leq 1.5 \times$ ULN unless participant is receiving anticoagulant therapy as long as the PT or aPTT is within the therapeutic range for the intended use of the anticoagulants

*Calculate serum creatinine clearance using the standard Cockcroft-Gault formula.
Abbreviations: ALT=alanine aminotransferase; AST=aspartate aminotransferase; GFR= glomerular filtration rate; INR=International Normalized Ratio; SGOT=serum glutamic oxaloacetic transaminase; SGPT= serum glutamic-pyruvic transaminase; ULN = upper limit of normal.

Participants for Cohort A

9. Must have been previously treated with fluoropyrimidine, irinotecan, and oxaliplatin.

Note: Adjuvant chemotherapy counts as a first line of prior systemic therapy if there is documented disease progression within 12 months of chemotherapy completion.

Participants for Cohorts B and C

10. Must not have received prior systemic chemotherapy for Stage IV CRC.

Note: Participants who have received adjuvant chemotherapy for non-Stage IV CRC and have documented disease progression within 12 months of chemotherapy completion will not be eligible as these participants may have relative resistance to the proposed 1L regimen, which may undermine the adequate efficacy assessment of this 1L combination.

Participants for Cohorts D and E

11. Must have been previously treated with 1 line of therapy including a fluoropyrimidine plus an oxaliplatin-based regimen.

Note: Adjuvant chemotherapy counts as 1 line of prior systemic therapy if there is documented disease progression within 12 months of chemotherapy completion.

Participants for Cohorts A, C, and E

12. Participants must have a 12-lead ECG and ECHO or MUGA scan performed by the investigator or other qualified person to evaluate cardiac function prior to enrollment in the study. Adequate cardiac function will be assessed by:

- a) LVEF $\geq 50\%$ as determined by MUGA scan or ECHO; and
- b) QT interval calculated according to the Fridericia method (QTcF) value ≤ 480 msec (mean of 3 measurements corrected for heart rate using Fridericia's formula).

Contraception

Male participants:

13. A male participant must agree to use a contraception as detailed in Appendix 5 of this protocol during the treatment period and for at least 180 days, after the last dose of study treatment and refrain from donating sperm during this period.

- a) Male participants with pregnant partners must agree to use a condom.
- b) No additional method of contraception is required for the pregnant partner.

Female participants:

14. A female participant is eligible to participate if she is not pregnant (see Appendix 6), not breastfeeding, and at least one of the following conditions applies:

- a) Not a woman of childbearing potential (WOCBP) as defined in Appendix 6 OR
- b) A WOCBP who agrees to follow the contraceptive guidance in Appendix 6 during the treatment period and for at least 180 days after the last dose of study treatment.

Informed Consent

15. The participant (or legally acceptable representative if applicable) provides written informed consent for the trial. The participant may also provide consent for Future Biomedical Research. However, the participant may participate in the main trial without participating in Future Biomedical Research.

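### The albumin limit in Table 4 is printed as at least 3.0 g/L, a level no realistic candidate can fail, so this row of the hepatic screen does not work as printed

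*Combined protocol and SAP*

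**What the plan says.** Section 6.1 opens with "Participants are eligible to be included in the study only if all of the following criteria apply", so each criterion binds. Criterion 8 reads "Have adequate organ function as defined in" Table 4, which carries the title "Table 4 Inclusion Criteria Laboratory Parameters". The Hepatic block of that table has three rows:

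- total bilirubin, with a direct-bilirubin alternative;
- AST and ALT, with a higher allowance for liver metastases;
- albumin, at 3.0 g/L or more.

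The Hematological block gives hemoglobin in two units, at least 9.0 g/dL or at least 5.6 mmol/L. A separate Coagulation block limits INR, PT or aPTT.

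The opening of Section 6 adds: "Prospective approval of protocol deviations to recruitment and enrollment criteria, also known as protocol waivers or exemptions, is not permitted".

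Elsewhere, albumin appears only as a listed chemistry analyte, in Table 11 (Section 9.5.6.1) and Table 13 (Appendix 3), with neither a limit nor a unit. Nothing in the documents restates or corrects the Table 4 row.

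**The concern.** An eligibility limit does its work only if some candidates could fall on the wrong side of it. A floor of 3.0 g/L looks too low for that by an order of magnitude.

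Two things are at stake. First, the sponsor chose to include albumin in the hepatic screen. Section 3.3.1.2 says that liver test abnormalities or liver toxicity may arise with any of the combinations, and Table 1 flags them for the three binimetinib cohorts. A row that excludes nobody removes one part of that screen.

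Second, the trial is multicenter and worldwide (Section 5.1), and the safety laboratory tests are done locally (Appendix 3). A site whose laboratory reports in g/L can compare its result directly with the printed limit and will pass everyone. A site whose laboratory reports in g/dL may read the 3.0 as being in its own unit and exclude some people. Eligibility could then depend on a laboratory's reporting convention.

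**Working it through.** **Inputs**

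- Albumin limit: 3.0 g/L (Table 4, Hepatic block).
- Hemoglobin limit: 9.0 g/dL or 5.6 mmol/L (Table 4, Hematological block).
- Conversion: 1 g/dL = 10 g/L.
- Adult serum albumin: assumed, because the documents give no range. About 35 to 50 g/L is taken as normal and about 10 to 30 g/L as low to severely low.
- Hemoglobin molar mass: 16.114 g/mmol (per monomer), assumed, for the control check only.

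**Step 1: control on the hemoglobin row.** 9.0 g/dL × 10 = 90 g/L, and 90 / 16.114 = 5.59 mmol/L, which rounds to the printed 5.6. The two hemoglobin units agree with each other, so that row is sound and its g/dL came through intact.

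**Step 2: convert the albumin row.** 3.0 g/L / 10 = 0.3 g/dL. Against the assumed range, 3.0 / 35 = 9% of the lower limit of normal, and 3.0 / 10 = 30% of a severely low value.

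**Step 3: who would be excluded.** The second limit below is what the same number would mean in g/dL (3.0 × 10 = 30 g/L). It is shown only to size the discrepancy.

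| Albumin (g/L) | Printed limit, 3.0 g/L | Same number read as g/dL, 30 g/L |
|---|---|---|
| 10 | pass | fail |
| 15 | pass | fail |
| 20 | pass | fail |
| 25 | pass | fail |
| 30 | pass | pass |
| 35 | pass | pass |
| 40 | pass | pass |
| 50 | pass | pass |

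Every value in the assumed range passes the printed limit, so the result does not depend on a precise choice of range.

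**Step 4: how much the unit could matter.** The documents give no albumin distribution, so three normal distributions are assumed for illustration. The share below a limit L is Φ((L − mean)/SD).

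| Assumed mean / SD (g/L) | Share below 3.0 g/L | z for 30 g/L | Share below 30 g/L |
|---|---|---|---|
| 40 / 5 | effectively 0 | −2.00 | 2.3% |
| 35 / 6 | effectively 0 | −0.83 | 20.2% |
| 30 / 7 | 0.006% | 0.00 | 50.0% |

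The printed limit excludes essentially nobody in all three cases. The alternative reading excludes anything from about 2% to 50%, depending wholly on the assumed population. The documents cannot narrow that range.

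**The case against.** The strongest reply is that this is a visible misprint with little consequence. Parts of that reply stand.

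- **The documents do not contradict themselves.** There is only one albumin limit. The unit error is inferred from the magnitude and from the hemoglobin row, and the inference rests partly on assumed physiology. This stands, although the inference holds over the whole assumed range.
- **The letter may have been lost in extraction.** Table 4 is available here only as text read from a PDF, and a dropped letter would produce exactly this row. The intact hemoglobin unit makes that less likely but does not rule it out. A check of the source settles it.
- **Other screens remain.** The bilirubin, AST/ALT and coagulation limits apply, as do ECOG 0 or 1 and a life expectancy of at least 3 months. This also stands: only one row is affected.

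A reader might be tempted by two stronger readings. The first is that inadequately screened participants would put disease-driven events into the DLT count. The documents do not support this. Section 5.1.3 requires at least a possible relation to study drug and excludes toxicities clearly not related to it, and no DLT criterion is tied to low albumin. The second is that the ban on waivers forces sites to apply 3.0 g/L literally. Section 6 bars prospective approval to enroll someone who fails a criterion. It does not show how sites read the row, or that they would not query it, and actual conduct is unknown.

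The misprint argument does not make the row work. It sits in a binding table, and nothing else in the documents supplies the intended limit.

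**Conclusion.** The point holds for one row of one table. As printed, the albumin limit is 0.3 g/dL and excludes effectively no candidate, on the assumption that adult albumin lies between about 10 and 50 g/L. The likely explanation is a unit wrong by a factor of 10. That remains an inference for the sponsor to confirm.

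The practical effect is a weakened hepatic screen and possible differences between sites according to their reporting unit. Neither can be quantified from the documents. The planning target of 159 participants, the mTPI dose-finding rules and the exact ORR intervals do not use this limit and are unaffected. It is a correction worth making because it concerns a binding eligibility threshold and is cheap. It is not a threat to the primary analysis.

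**What to change.** The sponsor should:

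1. check the albumin row of Table 4 against the source PDF;
2. if the row is printed there in the same way, confirm the intended limit and unit;
3. correct Table 4 by amendment or clarification letter, ideally stating the limit in both g/dL and g/L, as two units are already given for hemoglobin;
4. notify sites.

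No value is proposed here; the limit is the sponsor's to state. The edit is to a single table cell and needs no change to design or analysis. The downside is some additional screen failures if the corrected limit is higher than the printed one. Their number cannot be derived from the documents.
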